5. ANALYSIS POPULATIONS

The agreement and approval of subjects to be included/excluded from each analysis population will be established prior to database lock. The population definitions are as follows:

- **Enrolled population** will include all subjects who signed informed consent and met all screening criteria. The Enrolled population will be used for summaries of demographic and baseline disease characteristic.
- **Safety population** will consist of all subjects in the Enrolled population who receive at least one dose or partial dose of study drugs and have at least one post-dose safety observation recorded. The Safety population will be used for summaries and analyses of the safety and tolerability.
- **Pharmacokinetic (PK) population** will include all subjects in the Safety population who have at least one post-dose sample collected to allow estimation of the PK parameters. The PK population will be used for PK data analysis.

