13. STATISTICS

Summaries of continuous variables will present the number of subjects included in the analysis (N), the mean and standard deviation (SD), the median, the minimum, and the maximum statistics. Counts and percentages will be presented in summaries of categorical variables. The denominator for each percentage will be the number of subjects in the population unless otherwise specified. In general, missing data will not be imputed unless otherwise specified.

All disposition, baseline demographics and disease characteristics will be descriptively summarized for the Safety population

Analyses will be done separately for each study part and overall.

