13.3. Safety analyses

Safety analyses will be based on all subjects who receive at least 1 dose or partial dose of study drugs (Safety population). Drug exposure will be summarized using descriptive statistics. The severity of all adverse events is to be evaluated by the Investigator based on the National Cancer Institute (NCI) Common Terminology Criteria for Adverse Events (CTCAE) version 5.0 and verbatim terms will be coded to the preferred term (PT), higher level term (HLT), and system organ class (SOC) using the Medical Dictionary for Regulatory Activities (MedDRA) version in use at the time of the analysis. The number and percentage of subjects with adverse events will be presented by MedDRA SOC and PT, relationship to study treatment, and severity. Clinical laboratory values also will be classified by toxicity grade based on the NCI CTCAE, version 5.0. Laboratory shift tables from baseline result to the worst post-baseline result will be provided. AEs will be summarized separately for: AEs, serious AEs, AEs leading to discontinuation, AEs leading to death, Grade 3, or higher AEs (per NCI CTCAE Version 5.0). Physical examination, vital signs, 12-lead ECG, and ECOG performance status will be descriptively summarized based on marked abnormality criteria.

Analyses will be done separately for each study part and overall.

Complete details of the safety analysis will be provided in the statistical analysis plan (SAP).

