3.2. CHANGES TO ANALYSES FROM PROTOCOL

- According to Section 13.3 of the protocol (amendment 2.0), laboratory analytes will be summarized descriptively as value and change from baseline, as well as shifts from baseline (based on low, normal, high categorization) at each visit. To allow for more focused presentation of values most likely to represent a safety concern, laboratory analytes will be summarized as shift from the baseline to the worst post-baseline category (based on National Cancer Institute [NCI] Common Terminology Criteria for Adverse Events [CTCAE v5.0] severity grades).
- If warranted, additional exploratory analyses of safety endpoints may be performed.
- To be consistent with the analysis done in other studies and in the Integrated Summary of Safety (ISS), TEAEs with missing CTCAE grades will be treated as missing.

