10. MAJOR PROTOCOL DEVIATIONS

All protocol deviations will be listed for the safety population. Protocol deviations will be summarized by major and minor category and by study part. Predefined categories of major protocol deviations will include:

- Violation of inclusion/exclusion criteria

-
- Prohibited medications
 - Study drug compliance

Additional categories may be added during the course of the study but will be determined prior to database lock.

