11. DEMOGRAPHIC AND OTHER BASELINE CHARACTERISTICS

Demographic data and other baseline characteristics will be summarized by study part and overall, and listed for the Enrolled population. Demographics will include age (derived, in years), sex, race, ethnicity, and baseline characteristics will include, but not limited to, Eastern Cooperative Oncology Group (ECOG) performance status, complete physical examination, vital signs and drug/alcohol screening details.

Baseline disease characteristics will include tumor diagnosis (TD), prior anticancer therapy (yes/no), prior radiotherapy (yes/no), prior cancer related surgery (yes/no), progressive disease prior to study entry (yes/no), prior disease progression date of last progression prior to the study enrollment, blood smear (BS), Bone Marrow Aspirate/Biopsy (BM) and time from date of last disease progression to study entry (in months).

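### SAP 5 narrows the protocol's all-dosed Safety population to subjects who met every screening criterion and have a post-dose observation, and SAP 3.2 does not declare the change

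*SAP*

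**What the plan says.** Protocol 13.3, matched by the synopsis, sets one condition: "Safety analyses will be based on all subjects who receive at least 1 dose or partial dose of study drugs (Safety population").

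SAP 5 builds its populations in layers. Enrolled "will include all subjects who signed informed consent and met all screening criteria". Safety "will consist of all subjects in the Enrolled population who receive at least one dose or partial dose of study drugs" and, in addition, must "have at least one post-dose safety observation recorded". The PK population is then drawn from Safety.

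SAP 3.2 is headed "CHANGES TO ANALYSES FROM PROTOCOL". It has three items: laboratory shift tables, possible exploratory safety analyses, and missing CTCAE grades. None concerns an analysis population.

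SAP 10 states: "All protocol deviations will be listed for the safety population". It names breaches of eligibility criteria as a predefined major category.

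The two documents also assign baseline data to different sets. Protocol 13: "All disposition, baseline demographics and disease characteristics will be descriptively summarized for the Safety population". SAP 11: "Demographic data and other baseline characteristics will be summarized by study part and overall, and listed for the Enrolled population". Within the SAP, section 16 places every safety summary on Safety, while 16.3 places ECOG performance status on Enrolled.

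**The concern.** A safety set is normally defined by exposure so that nothing learned after dosing can remove a treated subject. SAP 5 makes membership depend on whether the subject satisfied the screening criteria. That can be revised after dosing, when an eligibility error comes to light. The SAP also adds an observation requirement that the protocol does not have.

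Following the protocol and following the SAP could therefore give different safety denominators from the same data, and nothing in SAP 3.2 tells a reader that a choice was made. Safety is a secondary objective in both parts, and each part is small, so a single subject is visible in the percentages. The change may also reach the primary objective, because the SAP nests the PK population inside Safety.

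**Working it through.** The plan gives no figure for this point. The check is a comparison of text, followed by arithmetic for scale.

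**1. The two definitions**

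| Condition for Safety | Protocol 13.3 and synopsis | SAP 5 |
|---|---|---|
| At least one full or partial dose | Yes | Yes |
| Signed consent and met all screening criteria (via Enrolled) | Not required | Required |
| Recorded post-dose safety observation | Not required | Required |

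The SAP set can equal the protocol set or be smaller; it cannot be larger. SAP 1 says the SAP follows protocol amendment 2.0. The first item in SAP 3.2 cites protocol 13.3, the section that defines the Safety population, yet the narrowing is not mentioned.

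**2. A subject dosed and later found to have failed a screening criterion, under the literal SAP rule**

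- SAP 5: not in Enrolled, so not in Safety or PK.
- SAP 16: absent from all safety summaries.
- SAP 13.2 and 14: absent from the medication, exposure and compliance summaries and listings.
- SAP 8: absent from the population counts, which are built on Enrolled.
- SAP 10: the eligibility violation is not listed, because deviations are listed for Safety only. The eligibility category could then hold only criteria breached after screening; the alcohol restriction, which runs through Cycle 1, is an example.
- SAP 16.1 and 16.2: the subject may remain in the AE and laboratory listings, which cover all AEs and all laboratory data.

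**3. Scale in the safety tables**

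Inputs: about 40 subjects enrolled, about 40% drop-out and 12 completers per part (protocol 7.2, SAP 4.2). An even split is assumed; it agrees with 12 / (1 − 0.40) = 20 per part.

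- One subject is 1/20 = 5% of a part and 1/40 = 2.5% overall.
- Illustrative event rate: protocol 5.5.1 reports 469 subjects with Grade 3 or 4 TEAEs among 895 treated, and 469/895 = 52.4%. The protocol prints 55% because its denominator is the 857 subjects with any TEAE. Rounded to whole subjects, take 10/20 = 50.0%.
- Remove one subject with an event: 9/19 = 47.4%, a change of −2.6 points.
- Remove one without an event: 10/19 = 52.6%, a change of +2.6 points.

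**4. Scale in the PK comparison, if the PK plan uses the SAP's PK population**

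The replacement triggers in protocol 8.2.4 are dose interruption or reduction, missed doses and missed PK samples. Later-found ineligibility is not among them. If the subject were one of the 12 planned completers, 11 would remain. For a paired comparison on the log scale, the 90% CI half-width is proportional to t(0.95, n − 1)/√n at equal SD:

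- n = 12: 1.796/3.464 = 0.518
- n = 11: 1.812/3.317 = 0.546
- Ratio: 1.054, so the interval is 5.4% wider.

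**The case against.** The strongest reply is that the Enrolled definition describes a gate, not a verdict in hindsight. Protocol 7.3 gives a subject number at enrolment to those who have satisfied the selection criteria, and eligibility is reconfirmed before Day 1 dosing. On that reading a subject who passed the gate stays Enrolled whatever is found later. SAP 10 supports this, since it expects eligibility violations among Safety subjects. SAP 5 also requires population membership to be agreed before database lock, and SAP 8 and 9 report membership, so an exclusion would probably be noticed. Protocol 13.3 leaves full details of the safety analysis to the SAP. The PK consequence depends on a separate plan not seen here. The event rate used for scale comes from pooled adult and paediatric monotherapy subjects and is only illustrative.

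Much of this bears on frequency, and there it stands: few subjects, perhaps none, would be affected. It does not repair the rule. SAP 5 never states the gate reading, so the tension with SAP 10 is a reason to clarify the text and cannot settle its meaning. Agreement before lock is a procedure without a criterion, and in an open-label study it would be applied with the safety data visible. Protocol 13.3 defers details but fixes the population itself, so narrowing it is a change. The gate reading also does nothing for the post-dose observation condition, although that one will rarely matter.

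**Conclusion.** The concern holds. SAP 5 adds two conditions to the protocol's Safety population and SAP 3.2 does not declare them. As written, the rule can remove dosed subjects from the safety denominators, and it sits at odds with SAP 10. That conclusion rests on the wording alone.

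The size of the effect is conditional. The documents do not say how many subjects would be removed, and the direction of any bias is not established. Under an even split, each removed subject is 5% of a part, and a rate near one half moves by 2.6 points. The 5.4% widening of the PK interval needs three further conditions: the subject is a planned completer, the PK plan adopts the SAP set, and the SD is unchanged.

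The baseline and ECOG discrepancies are separate and smaller, but they belong to the same set of unreconciled population rules. The point should be corrected before database lock.

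**What to change.** In SAP 5, define Safety as all subjects who receive at least one full or partial dose of any study drug, regardless of later-found ineligibility or the availability of post-dose observations, and do not make it a subset of Enrolled. State that later-found ineligibility does not remove a subject from Enrolled. Base the PK population on the dosed set, and pre-specify PK evaluability exclusions (for example, use of prohibited CYP3A4 modulators) in the PK analysis plan. Align SAP 11 with protocol 13, and SAP 16.3 with SAP 16.

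If the narrower Safety set is intended, declare and justify it in SAP 3.2.

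The cost is a few sentences in the SAP before database lock, with no new data and no burden on subjects.

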6. GENERAL CONSIDERATIONS

6.1. GROUPING OF SUBJECTS

Unless stated otherwise, subjects will be grouped and presented according to the study part and overall.

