2. STUDY OBJECTIVES AND ENDPOINTS

2.1. PRIMARY AND SECONDARY OBJECTIVES AND ENDPOINTS

Objectives	Endpoints
Part 1: Tazemetostat and Itraconazole	
Primary: 
 To evaluate the effect of CYP3A4 inhibition by itraconazole on the steady-state pharmacokinetics (PK) of tazemetostat when administered as a single and twice daily oral dose in subjects with advanced malignancies 	
 AUC_{0-t}: area under the plasma concentration-time curve from time 0 to the time of the last quantifiable concentration AUC_{0-72}: area under the plasma concentration-time curve from time 0 to 72 hours post-dose C_{max}: observed maximum plasma concentration
Secondary: 
 To evaluate the steady-state safety profile of tazemetostat when co-administered as a single and twice daily oral dose with itraconazole in subjects with advanced malignancies 	
 Safety parameters: Adverse event assessment, physical examination, vital signs (blood pressure, heart rate, body temperature), 12-lead ECG, clinical laboratory tests (hematology including coagulation profile, serum chemistries, urinalysis), ECOG performance status, and concomitant medication monitoring

 To evaluate the steady-state PK of tazemetostat and its metabolites after administration alone and with itraconazole To evaluate the effect of itraconazole on PK of a single 400 mg oral dose of tazemetostat. 	
 AUC_{0-t}: area under the plasma concentration-time curve from time 0 to the time of the last quantifiable concentration C_{max}: observed maximum plasma concentration T_{max}: observed time at C_{max} λ_z: terminal phase elimination rate constant $t_{1/2}$: terminal elimination half-life
Part 2: Tazemetostat and Rifampin	
Primary: 
 To evaluate the effect of CYP3A4 induction by rifampin on the steady-state PK of tazemetostat when administered as a single and twice daily oral dose in subjects with advanced malignancies 	
 AUC_{0-t}: area under the plasma concentration-time curve from time 0 to the time of the last quantifiable concentration AUC_{0-48}: area under the plasma concentration-time curve from time 0 to 48 hours post-dose

[figure not shown]
Objectives	Endpoints
	
 • C_{max}: observed maximum plasma concentration

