Secondary: 
 • To evaluate the steady-state safety profile of tazemetostat when co-administered as a single and twice daily oral dose with rifampin in subjects with advanced malignancies • To evaluate the steady-state PK of tazemetostat and its metabolites after administration alone and with rifampin. 	
 • Safety parameters: Adverse event assessment, physical examination, vital signs (blood pressure, heart rate, body temperature), 12-lead ECG, clinical laboratory tests (hematology including coagulation profile, serum chemistries, urinalysis), ECOG performance status, and concomitant medication monitoring • AUC_{0-t}: area under the plasma concentration-time curve from time 0 to the time of the last quantifiable concentration • C_{max}: observed maximum plasma concentration • T_{max}: observed time at C_{max} • λ_z: terminal phase elimination rate constant • $t_{1/2}$: terminal elimination half-life

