6.2.2. BASELINE ASSESSMENTS

Baseline data are defined as the last non-missing assessment (including unscheduled assessments) prior to starting treatment. If there is more than one value on or prior to starting treatment, the value closest to and prior to the receipt of the first dose, whether scheduled or unscheduled, will be used as the baseline value. Unless the collection time or label indicates otherwise, assessments performed on the same day as the first dose of study drug will be considered performed prior to the start of treatment. AEs and medications reported with a start date on the date of first dose will be considered to have occurred after the start of treatment. For vital signs (excluding weight and height) and ECG measures, baseline results will be identified for the set.

For laboratory parameters, the baseline time point will be determined separately for each parameter.

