7. STATISTICAL CONSIDERATIONS

Unless noted otherwise, the statistical considerations below will be applied and used for both study parts.

- As this is a phase I study, data from all centers will be pooled for analyses.
- Unless otherwise noted, table summaries will be presented by study part and overall.
- The issue of multiplicity will not apply to the endpoints for this study.
- Except for incomplete dates associated with AEs and medications (rules in [Appendix 1](#)) and missing severity or relationship (rules in Section 16.1), other missing safety data will not be imputed.
- Summary statistics will consist of the number and percentage of subjects in each category for discrete variables, and the number of subjects with non-missing values, mean, median, standard deviation (SD), minimum, and maximum for continuous variables.
- When the denominator includes subjects with missing values, a “missing” category may be added for completeness.
- In summary tables of continuous variables (except for weight, height and BMI), the minimum and maximum values will be displayed to the same number of decimal places as the raw data; all mean, median, and percentile values will be formatted to one more decimal place than the measured value. SD values will be formatted to two more decimal places than the measured value, unless otherwise specified. The maximum number of decimal places is 3 and values will be truncated to 3 decimal places in situations where there are more than 3 decimal places. Wherever possible data will be decimal aligned. For weight, height and BMI, only one decimal place will be kept for summary results (except N).

- All percentages will be rounded to one decimal place. The number and percentage of responses will be presented in the form XX (XX.X%).
- Change from baseline = test value at the post-baseline visit – baseline value. The percentage change from baseline will be calculated as (test value at the post-baseline visit - baseline value)/baseline value x 100. Percent of baseline is calculated as test value at the post-baseline visit/baseline value x 100. If either the baseline or the post-baseline value is missing, the change from baseline, percentage change from baseline, and percent of baseline are set to missing. If baseline is 0, then percentage of baseline and percentage change from baseline are set to missing.

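### No planned safety table isolates the co-administration period, although safety when co-administered is the secondary safety objective in both parts

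*SAP*

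**What the plan says.** **Objectives.** SAP 2.1 gives as a secondary objective for Part 1 "To evaluate the steady-state safety profile of tazemetostat when co-administered as a single and twice daily oral dose with itraconazole", and for Part 2 "To evaluate the steady-state safety profile of tazemetostat when co-administered as a single and twice daily oral dose with rifampin".

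**Grouping.** SAP 6.1: "Unless stated otherwise, subjects will be grouped and presented according to the study part and overall". SAP 7: "Unless otherwise noted, table summaries will be presented by study part and overall". Protocol 13.3: "Analyses will be done separately for each study part and overall".

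**Baseline and time frame.** Under SAP 6.2.2, "the value closest to and prior to the receipt of the first dose, whether scheduled or unscheduled, will be used as the baseline value", so each measure has one reference value, taken before any study drug. SAP 16.1 defines one TEAE window, from the first dose to 30 days after the end of study drug or the start of a later anticancer therapy. SAP 3.2 says "laboratory analytes will be summarized as shift from the baseline to the worst post-baseline category". SAP 16.2, 16.4 and 16.5 use worst post-baseline values for laboratory tests, QTcF and vital signs, and SAP 16.3 uses best and worst values for ECOG.

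**Denominator.** The Safety population in SAP 5 is enrolled subjects who "receive at least one dose or partial dose of study drugs and have at least one post-dose safety observation recorded".

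**Later cycles.** SAP 4.1.2 makes the inclusion of safety data from all cycles, in the report or an addendum, depend on what is available at the primary analysis.

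**The concern.** The objective concerns one stretch of Cycle 1, and the tables cover the whole time on study. In Part 1 the main safety tables mix tazemetostat 400 mg alone, itraconazole alone (Days 18–20), co-administration, off-drug follow-up and any available Cycle 2+ data at 800 mg twice daily. In Part 2 they mix tazemetostat alone, co-administration with rifampin, follow-up and any available Cycle 2+ data.

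A reader of the study report could not take from any planned table the incidence of events, the worst laboratory grade, the QTcF shift or the vital sign abnormalities during co-administration. Subjects who received a first dose but left before the first co-administered dose would still count in every percentage. The study rationale (Protocol 5.3) expects the second drug to raise or lower tazemetostat exposure, so this is the period whose safety the reader will want to see.

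**Working it through.** **1. Is a period split stated anywhere?** The SAP 6.1 default gives way to a statement elsewhere, so each candidate needs checking.

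| Place | What it provides | Incidence during co-administration? |
|---|---|---|
| SAP 6.2.3 | Convention for by-visit summaries | No; SAP 16 plans no by-visit safety table |
| SAP 16.1 | Related TEAEs by each study drug | No; this is attribution, not time of onset |
| SAP 16.2–16.5 | Worst (ECOG: best and worst) post-baseline values | No |
| SAP 14.1, 14.2 | Tazemetostat amount and compliance, Cycle 1 versus later | No; exposure only, and Cycle 1 itself mixes periods |
| SAP 3.2 | Exploratory safety analyses, if warranted | None defined |
| Listings | Dates, in some cases study day | Only by hand |

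By contrast, Protocol 13.2 summarises PK concentrations by treatment and day.

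**2. Length of the second-drug periods.** SAP 14.1 uses totals of 4200 mg itraconazole and 5400 mg rifampin. From Protocol 7.3, Days 18–38 are 21 days and 21 × 200 = 4200 mg; Days 17–25 are 9 days and 9 × 600 = 5400 mg. Both totals reproduce.

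**3. Share of time.** Co-administration is counted from the first joint dose to the last itraconazole or rifampin dose: Days 21–38 = 18 days, and Days 17–25 = 9 days. For a subject who stops after Cycle 1 and starts no new anticancer therapy, the TEAE window ends on Day 38 + 30 = 68, or Day 25 + 30 = 55.

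| | Part 1 | Part 2 |
|---|---|---|
| Share of Cycle 1 | 18/39 = 46% | 9/26 = 35% |
| Share of TEAE window | 18/68 = 26% | 9/55 = 16% |
| Days with both drugs dosed, share of window | 16/68 = 24% | 8/55 = 15% |
| Window share with three later cycles (assumption) | 18/(39+84+30) = 18/153 = 12% | 9/(26+84+30) = 9/140 = 6% |

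If the window is counted from the last tazemetostat dose (Day 36 or Day 24), the shares are 18/66 = 27% and 9/54 = 17%.

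**4. Scheduled Cycle 1 assessments after the first dose** (Protocol Tables 3 and 4, footnotes k and n).

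- ECGs, Part 1: Day 1 at 2 h, Day 3, Day 15 twice and Day 17 (5, tazemetostat alone); Day 21 pre-dose (1, itraconazole alone); Day 21 at 2 h, Day 22, Days 25, 28, 31, 34 and 36 twice each, and Day 38 (13). Co-administration: 13 of 19.
- ECGs, Part 2: Day 1 at 2 h, Day 3, Day 15 twice and Day 17 pre-dose (5); Day 17 at 2 h, Days 19, 21 and 24 twice each, and Day 26 (8). Co-administration: 8 of 13.
- Laboratory draws, assumed taken before that day's dose. Part 1: Days 3, 15, 18, 21, 22, 36 and 39, of which Days 22, 36 and 39 count. The 24-hour allowance lets the Day 22 draw be taken on Day 21, possibly before dosing, so 2 to 3 of 7. Part 2: Days 3, 15, 17, 24 and 26, of which Days 24 and 26 count, so 2 of 5.

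The closing assessments (ECG on Day 38 or 26, laboratory draw on Day 39 or 26) come 48 or 72 hours after the last tazemetostat dose, so counting them is a choice of definition. Without them the counts are 12 of 19 and 7 of 13 ECGs, and 1–2 of 7 and 1 of 5 draws.

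**5. Denominator.** SAP 4.2 plans about 40 enrolled and 24 completed, so about 16 do not complete. The timing of drop-out is not given. The number dosed but never co-administered therefore lies somewhere between 0 and about 16.

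**The case against.** **The SAP follows the protocol.** Protocol 13.3 asks for safety by part and overall, and the SAP does that. Each part uses only one second drug, so the part split already separates itraconazole from rifampin. This stands: the SAP does not depart from the protocol. Both documents, however, group the data in a way that does not answer the objective they state.

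**Small, confounded data.** With about 12 completers per part and a fixed sequence, period is tied to time and disease course. This stands as a limit on comparing periods. It does not bar describing one of them.

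**The data can be recovered.** Listings and attribution tables exist. Listings do allow reconstruction by hand at this sample size. Attribution does not help: an event caused by raised tazemetostat exposure would be attributed to tazemetostat, as would one arising on tazemetostat alone.

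**The worst case already reflects co-administration.** In Cycle 1, 13 of 19 and 8 of 13 post-dose ECGs fall in that period, so the Cycle 1 worst QTcF draws mostly on it. This is fair, and it is why the 26% and 16% shares should not be read alone. The table still cannot show in which period the worst value arose.

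**A stronger reading a reader might infer** is that every safety table mixes co-administration with Cycle 2+ dosing. The documents do not support that. SAP 4.1.2 leaves open how much Cycle 2+ data will be included. Protocol 7.5.1 does not allow tazemetostat dose reductions in Cycle 1, so the table of TEAEs leading to dose reduction is in effect a Cycle 2+ table.

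**Conclusion.** The gap is real and concerns presentation. No planned safety table reports incidence during co-administration, which is the subject of the secondary safety objective in each part. The main tables place that period in a pool of which it forms 26% (Part 1) or 16% (Part 2) of the TEAE window for a subject who stops after Cycle 1, and less as cycles are added. Within Cycle 1 alone the shares are 46% and 35%.

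The figures rest on the planned dosing days, no new anticancer therapy, and co-administration counted to the last itraconazole or rifampin dose. They describe scale. A reader might take them as a measure of bias or dilution in event rates, but the documents give no event rates by period from which that could be worked out. Nor do they show that safety during co-administration is unrecoverable, or that the primary PK comparison is affected. It is worth correcting before database lock, because the schedule already collects the data.

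**What to change.** In SAP 6.1 and 16, keep the pooled columns. Within each part, but not in the overall column, also summarise by treatment period, using actual dose dates: the overall TEAE, grade 3 or 4 TEAE and SAE tables, worst laboratory grade, QTcF, vital signs and worst ECOG.

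- **Periods:** tazemetostat alone; itraconazole alone (Part 1, TEAEs only); co-administration; Cycle 2+; follow-up. For all subjects, co-administration runs from the first co-administered dose through the end-of-Cycle-1 assessments (Day 39 or Day 26), or the day after the last Cycle 1 study drug dose if earlier. Events starting in any gap before a late first Cycle 2 dose go with follow-up.
- **Assignment:** TEAEs by recorded start date, and by worsening only where a dated record of worsening exists. Protocol 12.4.1.1 requires a new record only for worsening of a pre-treatment event, and Protocol 12.6 lists onset and resolution but no worsening date. Same-day pre-dose assessments go to the preceding period by actual collection time. Cycle 2 Day 1 pre-dose values go to no treatment period.
- **Denominator:** subjects dosed in that period.
- **Reference value:** for co-administration, also give change from the last value before the first itraconazole or rifampin dose.
- **Caveat to state:** comparisons between periods are descriptive, because the sequence is fixed, periods differ in length and number of assessments, early co-administration days precede steady state, and effects of itraconazole or rifampin may carry over into early Cycle 2.

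Cost: SAP wording and about eight extra tables (three AE, one laboratory, two QTcF, one vital signs, one ECOG). No new data collection is needed. The drawback is small counts per period.
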